Clinical Trial Protocol

| | |
|---|--|
| Document Number: c19596566-03 | |
| EudraCT No.: | 2017-003853-41 |
| BI Trial No.: | 1386-0019 |
| BI Investigational Product: | BI 1467335 |
| Title: | A phase I, open-label, single-arm multiple dose trial to investigate pharmacokinetics and absolute bioavailability of BI 1467335 administered as an oral dose simultaneously with an intravenous microtracer dose of [C-14] BI 1467335 after single and multiple oral doses in healthy male volunteers |
| Lay Title: | This study in healthy men tests how the body takes up BI 1467335 |
| Clinical Phase: | I |
| Trial Clinical Monitor: | 
Phone: Fax:
 |
| Principal Investigator: | 
Phone: Fax:
 |
| Status: | Final Protocol (Revised Protocol (based on global amendment 2)) |
| Version and Date: | Version: 3.0 Date: 24 April 2018 |
| Page 1 of 65 | |
| Proprietary confidential information © 2018 Boehringer Ingelheim International GmbH or one or more of its affiliated companies. All rights reserved. This document may not - in full or in part - be passed on, reproduced, published or otherwise used without prior written permission | |

CLINICAL TRIAL PROTOCOL SYNOPSIS

| | | | |
|---|-----------------------------------|---|--|
| Name of company: Boehringer Ingelheim | | Tabulated Trial Protocol | |
| Name of finished product: Not applicable | | | |
| Name of active ingredient: BI 1467335 | | | |
| Protocol date: 16 February 2018 | Trial number: 1386-0019 | | Revision date: 24 April 2018 |
| Title of trial: A phase I, open-label, single-arm multiple dose trial to investigate pharmacokinetics and absolute bioavailability of BI 1467335 administered as an oral dose simultaneously with an intravenous microtracer dose of [C-14] BI 1467335 after single and multiple oral doses in healthy male volunteers | | | |
| Principal Investigator: | | | |
| Trial site: | | | |
| Clinical phase: I | | | |
| Objectives: | | To investigate the pharmacokinetics and absolute bioavailability of BI 1467335 with an intravenous formulation containing labelled [C-14] BI 1467335 and an unlabelled oral tablet formulation of BI 1467335 in healthy male subjects | |
| Methodology: | | Non-randomised, open-label, single arm multiple dose design | |
| No. of subjects: | | | |
| total entered: | | 12 | |
| each treatment: | | At least 10 enrolled subjects, maximum 12 enrolled subjects | |
| Diagnosis: | | Not applicable | |
| Main criteria for inclusion: | | Healthy male subjects, age of 18 to 65 years, body mass index (BMI) of 18.5 to 29.9 kg/m ² | |
| Test product 1 (T1): | | BI 1467335 film-coated tablet formulation | |
| dose: | | 10 mg of free base (2 x 5 mg) QD | |
| mode of admin.: | | Oral with 240 mL of water | |

| | | | |
|--|--|-------------------------------------|--|
| Name of company: Boehringer Ingelheim | | Tabulated Trial Protocol | |
| Name of finished product: Not applicable | | | |
| Name of active ingredient: BI 1467335 | | | |
| Protocol date: 16 February 2018 | Trial number: 1386-0019 | | Revision date: 24 April 2018 |
| Test product 2 (T2): | Unlabelled BI 1467335 mixed with Carbon 14 labelled BI 1467335 [BI 1467335 (C-14)] as an intravenous infusion | | |
| dose: | 
 – On Day 1 50 µg infusion consisting of 41.15 µg unlabelled BI 1467335 free base (= 46.50 µg salt) mixed with 8.85 µg [C-14] BI 1467335 free base (=10 µg salt) in 10 mL solution (5 µg BI 1467335 (C-14) free base /mL) – On Day 28 50 µg infusion consisting of 45 µg unlabelled BI 1467335 free base (=50,85 µg salt) mixed with 5 µg [C-14] BI 1467335 free base (=5,65 µg salt) in 10 mL solution (5 µg BI 1467335 (C-14) free base /mL) 
The radioactive dose per infusion has been selected to not exceed 2.7 µCi=0.1 MBq.
 | | |
| mode of admin.: | Intravenous infusion | | |
| Comparator product: | Not applicable | | |
| Duration of treatment: | 
Intravenous dose (reference): A single 15 minutes intravenous infusion of the microtracer on Day 1 and Day 28.
 
Oral dose (test): Non-radiolabelled film-coated tablets once a day from Day 1 to Day 28 (treatment duration 28 days)
 | | |
| Criteria for pharmacokinetics: | 
Primary endpoints:
 
After the first dose: C_{max} and $AUC_{0-\infty}$ of BI 1467335 (after intravenous and oral administration) on Day 1
 
After multiple doses: $C_{max, 28}$ and $AUC_{0-24, 28}$ of BI 1467335 (after oral administration) on Day 28; $C_{max, 28}$ and $AUC_{0-\infty, 28}$ of BI 1467335 (after intravenous administration) on Day 28.
 
Secondary endpoints:
 
Assessment of the oral pharmacokinetics following intravenous treatment with a microtracer of [C-14] BI 1467335 and a treatment with BI 1467335 film-coated tablets in plasma:
 
Oral: t_{max}, $t_{max, 28}$, $t_{1/2}$
 
IV: CL, CL_{28}, V_z, $V_{z, 28}$, t_{max}, $t_{max, 28}$, $t_{1/2}$, $t_{1/2, 28}$
 
Further pharmacokinetic assessments will be included as appropriate based on emerging data.
 | | |

| | | | |
|--|---|-------------------------------------|--|
| Name of company: Boehringer Ingelheim | | Tabulated Trial Protocol | |
| Name of finished product: Not applicable | | | |
| Name of active ingredient: BI 1467335 | | | |
| Protocol date: 16 February 2018 | Trial number: 1386-0019 | | Revision date: 24 April 2018 |
| Criteria for safety: | Adverse events (AEs) including clinically relevant findings from the physical examination, safety laboratory tests, 12-lead electrocardiogram (ECG), vital signs (blood pressure [BP], pulse rate [PR]) | | |
| Statistical methods: | 
Absolute bioavailability (F) will be estimated by the ratio of the geometric means (tablet/infusion) for the dose normalized primary endpoints separately for Day 1 and Day 28. Additionally, its two-sided 90% confidence interval (CI) will be provided. This method corresponds to the two one sided t-tests procedure, each at the 5% significance level. Since the main focus is on estimation and not testing, an acceptance range was not specified. The statistical model will be an ANOVA on the logarithmic scale including the fixed effect for 'formulation' and 'subject' as a random effect. CIs will be calculated based on the residual error from ANOVA.
 
In addition, the absolute bioavailability factor F will be calculated for each subject on Day 1 and Day 28.
 
Descriptive statistics will be calculated for all endpoints.
 | | |

FLOW CHART

| Visit | Day | Planned time (relative to first oral drug administration [h:min]) | Approximate clock time of actual day [h:min] | Event and comment | Safety laboratory | PK _{plasma} | PK _{plasma} [C-14]BI1467335 | 12-lead ECG | Vital signs (BP, PR) | Questioning for AEs and concomitant therapy | |
|-------|-----------|---|--|--|--|----------------------|--------------------------------------|----------------|----------------------|---|----------------|
| 1 | -21 to -2 | | | Screening (SCR) ¹ | x | | | x | x | | |
| 2 | -1 | -18:00 | 14:00 | Admission to trial site | x ⁵ | | | | | ↑ ↓ | |
| | | 1 | -2:00 | 06:00 | | x ^{2,4} | x ^{2,8} | x ² | x ² | | x ² |
| | | | 0:00 | 08:00 | Drug administration (film coated tablet of BI 1467335) | | | | | | |
| | | 0:15 | 08:15 | | | x | | | | | |
| | | 0:30 | 08:30 | | | x | | | | | |
| | | 0:45 | 08:45 | | | x | | | | | |
| | | 1:00 | 09:00 | Start of 10 mL 50 µg infusion consisting of 41.15 µg unlabelled BI 1467335 and 8.85 µg [C-14] BI 1467335 | | | | | | | |
| | | 1:05 | 09:05 | | | x | x | | | | |
| | | 1:15 | 09:15 | End of infusion | | | x | | | | |
| | | 1:25 | 09:25 | | | x | x | | | | |
| | | 1:35 | 09:35 | | | | x | | | | |
| | | 1:45 | 09:45 | | | | x | | | | |
| | | 2:00 | 10:00 | 240 mL water intake | | x | x | x | | | |
| | | 2:15 | 10:15 | | | | x | | | | |
| | | 2:45 | 10:45 | | | | x | | | | |
| | | 3:00 | 11:00 | | | x | | | | | |
| | | 3:15 | 11:15 | | | | x | | | | |
| | | 3:45 | 11:45 | | | | x | | | | |
| | | 4:00 | 12:00 | Lunch, 240 mL water intake ³ | | x | | | | | |
| | | 4:15 | 12:15 | | | | x | | | | |
| | | 4:45 | 12:45 | | | | x | | | | |
| | | 5:15 | 13:15 | | | | x | | | | |
| | | 6:00 | 14:00 | | | x | | | | | |
| | | 6:15 | 14:15 | | | | x | | | | |
| | | 7:15 | 15:15 | | | | x ¹⁰ | | | | |
| | | 8:00 | 16:00 | | | x | | | | | |
| | 8:15 | 16:15 | | | | x ¹⁰ | | | | | |
| 9:15 | 17:15 | | | | x ¹⁰ | | | | | | |
| 10:00 | 18:00 | Dinner ³ | | | | | | | | | |
| 13:00 | 21:00 | | | | x ¹⁰ | | | | | | |
| 2 | 2 | 24:00 | 08:00 | Dispense of study medication | | | | x | x | | |
| | | 25:00 | 09:00 | Discharge from trial site ⁷ | | | x ¹⁰ | | | | |

| Visit | Day | Planned time (relative to first oral drug administration [h:min]) | Approximate clock time of actual day [h:min] | Event and comment | Safety laboratory | PK _{plasma} | PK _{plasma} [C-14]BI1467335 | 12-lead ECG | Vital signs (BP, PR) | Questioning for AEs and concomitant therapy |
|--------|--------|---|--|--|-------------------|----------------------|--------------------------------------|----------------|----------------------|---|
| 2 | 6 | 132:00 | 20:00 | Admission to trial site | x ³ | | | | | ↑ |
| | 7 | 144:00 | 08:00 | Dispense of study medication, discharge ⁷ | | x ² | | x ² | x ² | |
| | 13 | 300:00 | 20:00 | Admission to trial site | x ⁵ | | | | | |
| | 14 | 312:00 | 08:00 | Dispense of study medication, discharge ⁷ | x ² | x ² | | x ² | x ² | |
| | 20 | 468:00 | 20:00 | Admission to trial site | x ⁵ | | | | | |
| | 21 | 480:00 | 08:00 | Dispense of study medication, discharge ⁷ | | x ² | | x ² | x ² | |
| | 25 | 582:00 | 14:00 | Admission to trial site ¹¹ | x ⁵ | | | | x | |
| | 26 | 600:00 | 08:00 | Drug administration (film coated, of BI 1467335) | | | | | | |
| | 27 | 624:00 | 08:00 | Drug administration (film coated, of BI 1467335) | | | | | | |
| | 28 | 646:00 | 06:00 | | x ^{2, 4} | | | x ² | x ² | |
| | | 647:55 | 07:55 | | | x | x | | | |
| | | 648:00 | 08:00 | Drug administration (film coated, of BI 1467335) | | | | | | |
| | | 648:15 | 08:15 | | | x | | | | |
| | | 648:30 | 08:30 | | | x | | | | |
| | | 648:45 | 08:45 | | | x | | | | |
| | | 649:00 | 09:00 | Start of 10 mL 50 µg infusion consisting of 45 µg unlabelled BI 1467335 and 5 µg [C-14] BI 1467335 | | | | | | |
| | | 649:05 | 09:05 | | | x | x | | | |
| | | 649:15 | 09:15 | End of infusion | | | x | | | |
| | | 649:25 | 09:25 | | | x | x | | | |
| | | 649:35 | 09:35 | | | | x | | | |
| | | 649:45 | 09:45 | | | | x | | | |
| | | 650:00 | 10:00 | 240 mL water intake | | x | x | | | |
| | | 650:15 | 10:15 | | | | x | | | |
| | | 650:45 | 10:45 | | | | x | | | |
| | | 651:00 | 11:00 | | | x | | | | |
| | | 651:15 | 11:15 | | | | x | | | |
| | | 651:45 | 11:45 | | | | x | | | |
| | | 652:00 | 12:00 | Lunch, 240 mL water intake ³ | | x | | | | |
| | | 652:15 | 12:15 | | | | x | | | |
| | 652:45 | 12:45 | | | | x | | | | |
| | 653:15 | 13:15 | | | | x | | | | |
| | 654:00 | 14:00 | | | x | | | | | |
| 655:15 | 15:15 | | | | x | | | | | |
| 656:00 | 16:00 | | | x | | | | | | |
| 657:15 | 17:15 | | | | x | | | | | |
| 658:00 | 18:00 | Dinner ³ | | x | | | | | | |

| Visit | Day | Planned time (relative to first oral drug administration [h:min]) | Approximate clock time of actual day [h:min] | Event and comment | Safety laboratory | PK _{plasma} | PK _{plasma} [C-14]BI1467335 | 12-lead ECG | Vital signs (BP, PR) | Questioning for AEs and concomitant therapy |
|-------|-------|---|--|--|-------------------|----------------------|--------------------------------------|-------------|----------------------|---|
| 2 | 28 | 660:00 | 20:00 | | | X | | X | X | ↑ ↓ |
| | | 661:00 | 21:00 | | | | X | | | |
| | 29 | 672:00 | 08:00 | | | X | | | | |
| | | 673:00 | 09:00 | | | | X | | | |
| | 30 | 697:00 | 09:00 | | X | | X | X | X | |
| | 32 | 745:00 | 09:00 | Discharge from trial site | | | X | | | |
| 3 | 33-40 | | | End of trial (EOT) examination ^{6, 9} | X | | | X | X | X |

1. Screening includes subject information, informed consent, physical examination, check of vital signs, ECG, safety laboratory (including drug and virus screening), demographics (including determination of body height and weight, BMI, smoking status and alcohol history), relevant medical history, concomitant therapy and review of inclusion/exclusion criteria.
2. The time is approximate; the procedure is to be performed within a time window of 3 h prior to drug administration. After start of treatment, further PK blood sampling (trough level) within 30 minutes before next scheduled dosing.
3. If several actions are indicated at the same time point, the intake of meals will be the last action.
4. Subjects are to be fasted for at least 10 h before sample is taken.
5. Only urine drug and alcohol screening will be done at this time point.
6. End-of-trial (EOT) examination to be performed on Day 34-41, EOT examination includes physical examination, vital signs, ECG, safety laboratory, recording of AEs and concomitant therapies.
7. On Days 3 to 6, 8 to 13, 15 to 20 and 22 to 25, subjects are allowed to take their study medication at home if deemed appropriate by the investigator. Compliance of medication intake will be monitored by subject diary and daily phone contact between subject and site. The scheduled time for drug intake throughout the study is 08:00 (applies for intake at home and at the trial site).
8. Pharmacogenomic sample.
9. For definition of the individual subject's end of trial see [Section 6.2.3](#).
10. Samples for an individual subject beyond 5 h after end of infusion will be only analyzed if for this subject the plasma level of [C-14]BI 1467335 at this time point (i.e., 6:15) is still above LOQ.
11. Subjects will be hospitalized from admission on Day 25 to Day 32.

TABLE OF CONTENTS

| | |
|--|-----------|
| TITLE PAGE | 1 |
| CLINICAL TRIAL PROTOCOL SYNOPSIS | 2 |
| FLOW CHART | 5 |
| TABLE OF CONTENTS | 8 |

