2. RATIONALE, OBJECTIVES, AND BENEFIT - RISK ASSESSMENT

2.1 RATIONALE FOR PERFORMING THE TRIAL

This trial is intended to examine the absolute oral bioavailability of BI 1467335 using an iv [C-14] microtracer approach. The data are considered necessary to further support the understanding of the pharmacokinetics of BI 1467335. Due to the time dependent non-linear kinetics of BI 1467335, systemic exposures on Day 28 cannot be predicted from Day 1 kinetics, (IB [[c04751792](#)]). Therefore absolute oral bioavailability using an iv [C-14] microtracer dose will be determined on Day 1 and on Day 28 following a single (Day 1) and multiple dose treatment (Day 1 to 28) with an oral unlabelled dose of 10 mg of BI 1467335 q.d.

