4.2.2.2 Restrictions on diet and life style

While admitted to the trial site the subjects are restricted from consuming any other foods or drinks than those provided by the staff. Standardised meals will be served at the time points

described in the [Flow Chart](#). In addition, subjects are required to refrain from smoking while hospitalized.

On Day 1 and Day 28 starting from 1 hour before drug administration until 2 h after drug intake fluid intake is not allowed except from the 240 mL water administered with the drug intake and an additional 240 mL of water served on Day 1 and Day 28 at 2 h post-dose (mandatory for all subjects). From 2 hours until 22 hours post-dose fluid intake should be within about 1000 to 3000 mL.

On Day 1 and Day 28 subjects will receive a 15 minutes microtracer infusion 1 h after intake of film-coated tablets (i.e., t_{max} for oral dose). The handling instructions will be filed in the ISF.

Poppy-seed containing products should not be consumed starting 2 days before first trial drug administration until last PK sampling of the trial.

For fasting times before drug administration see [Section 4.1.4](#). For fasting times before safety laboratory investigations see [Section 5.2.3](#).

Grapefruits, Seville oranges (sour or bitter oranges) and their juices, and dietary supplements and products including St. John's wort (*Hypericum perforatum*) are not permitted starting 7 days before the first administration of trial medication until after the last PK sample is collected.

Alcoholic beverages are not allowed 48 hours before administration of the compound, before each admission and during the clinic period. During ambulatory phases alcohol consumption is restricted to 24 units a week.

Methylxanthine-containing drinks or foods (such as coffee, tea, cola, energy drinks, and chocolate) are not allowed at days of inhouse confinement.

Subjects should be advised to avoid foods containing a very large amount of tyramine (especially found in fermented food) while taking BI 1467335. These include for example aged cheese, aged meats, soybean products (soy sauce), red wine, tap (draft) beer, St John's Wort, pickled herring, sauerkraut (fermented cabbage), and tryptophan supplements.

Excessive physical activity (such as competitive sport) should be avoided starting 4 days before the first administration of trial medication until the end of trial examination.

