6.2.2 Treatment period

Each subject will receive on Day 1 a single 10 mL infusion of 50 μg BI 1467335 (C-14) (containing 8,85 μg [C-14] BI 1467335 free base and 41,15 μg of BI 1467335 free base) over a period of 15 minutes, 1 h after oral intake of 10 mg of BI 1467335 (film-coated tablets). All subjects will continue to receive a single oral dose of 10 mg BI 1467335 from Day 2 up to Day 28. On Day 28 all subjects will again receive a single 10 mL infusion of 50 μg BI 1467335 (C-14) (containing 5 μg [C-14] BI 1467335 free base and 45 μg of BI 1467335

free base) over a period of 15 minutes, 1 h after oral intake of 10 mg of BI 1467335 free base (film-coated tablets).

On Day 6, Day 13 and Day 20 (due to assessments and dispensing of study medication in the morning of the next day) participants will be admitted to the trial site and kept under close medical surveillance as indicated in the [Flow Chart](#) and [Section 5.2.5](#).

For details on time points and procedures for collection of plasma samples for PK analysis, refer to [Flow Chart](#) and [Section 5.5.2](#).

The safety measurements performed during the treatment period are specified in [Section 5.2](#) of this protocol and in the [Flow Chart](#). For details on time points for all other trial procedures, refer to the [Flow Chart](#). AEs and concomitant therapy will be assessed continuously from screening until the end of trial examination.

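### The last Day 1 tracer sample (25:00) falls 1 h after the second 10 mg tablet; drawing it just before that tablet would remove an avoidable ambiguity from Day 1 iv AUC0-inf, CL and F

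*Protocol*

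**What the plan says.** The Day 2 part of the protocol Flow Chart has two rows. The first reads "24:00 | 08:00 | Dispense of study medication" and carries no plasma or tracer sample. The second reads "25:00 | 09:00 | Discharge from trial site" and carries the last [C-14] sample of the Day 1 profile.

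The time of the Day 2 tablet has to be assembled from other places:

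- Flow Chart footnote 7: "The scheduled time for drug intake throughout the study is 08:00 (applies for intake at home and at the trial site".
- The same footnote on home intake: "On Days 3 to 6, 8 to 13, 15 to 20 and 22 to 25, subjects are allowed to take their study medication" at home. Day 2 is not in that list.
- Section 6.2.2: "All subjects will continue to receive a single oral dose of 10 mg BI 1467335 from Day 2 up to Day 28".

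Footnote 10 makes the late tracer samples conditional: "Samples for an individual subject beyond 5 h after end of infusion will be only analyzed if for this subject the plasma level" at 6:15 is still above LOQ. Section 4.2.2.2 describes a "15 minutes microtracer infusion 1 h after intake of film-coated tablets (i.e., t_{max} for oral dose", so the protocol takes oral tmax as 1 h. Section 2.1 states: "Due to the time dependent non-linear kinetics of BI 1467335, systemic exposures on Day 28 cannot be predicted from Day 1 kinetics".

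After the iv dose, AUC0-inf on Day 1 is a primary endpoint (Section 5.5.1.1). It is also the denominator of Day 1 F (Sections 5.5.1.2 and 7.3.5).

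**The concern.** The Day 1 iv profile is meant to describe the tracer after one oral dose. Its last point is taken at the expected peak of a second oral dose, and no tracer sample lies between 13:00 and 25:00. That point therefore closes the longest interval of the profile and largely sets the terminal slope. Any effect of the second tablet on the tracer would pass into iv AUC0-inf, CL, t1/2, Vz and Day 1 F.

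Neither document says whether 25:00 is drawn before or after the tablet, cuts the Day 1 iv profile at 24 h, or says how this sample enters the slope. Footnote 2 asks for trough samples before the next dose, but it is not attached to the 25:00 sample.

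**Working it through.** **Timing.** The Flow Chart's time base reproduces. Infusion end 1:15 + 5:00 = 6:15, as in footnote 10. First tablet 08:00 + 24 h = 08:00 on Day 2, and + 25 h = 09:00. Hence 25:00 - 24:00 = 1:00 h after the second tablet, equal to the protocol's oral tmax. Of the 19 planned Day 1 tracer samples after infusion start, only this one follows the second dose.

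**What the tablet can do.** It is unlabelled, and the tracer is measured as C-14 by AMS (Section 5.5.3.1). The tablet cannot add to the signal; it can only change how the tracer is distributed or eliminated.

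**Weight of the point.** Assume a log-linear slope on the last three samples: 9:15, 13:00 and 25:00 (9.25, 13 and 25 h).

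- Mean time = 15.75 h.
- Sxx = 6.5² + 2.75² + 9.25² = 135.375.
- Leverage of 25:00 = 1/3 + 9.25²/135.375 = 0.97.
- Multiplying the 25:00 value by f lowers lambda-z by ln(f) × 9.25/135.375 = 0.0683 × ln(f) per hour.

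**Worked case: half-life 8 h, f = 1.10, mono-exponential decline after a 15-min infusion.**

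- lambda-z: 0.0866 - 0.0683 × 0.0953 = 0.0801 per h, so t1/2 rises by 8.1%.
- Extrapolated part: 12.64% of AUC becomes 12.64 × 1.10 × 1.0813 = 15.03%, a gain of 2.39 points.
- Interval 13:00 to 25:00 (23.10% of AUC, log trapezoid): rises by a factor of 1.0407, a gain of 0.94 points.
- AUC0-inf: +3.3%. F and CL: 1/1.033 - 1 = -3.2%.

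**Same method over assumed half-lives**, with only the 25:00 value changed:

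| Assumed t1/2 | AUC0-inf at +10% / -10% | F at +10% / -10% | t1/2 at +10% / -10% |
|---|---|---|---|
| 2 h | +0.04% / -0.04% | -0.04% / +0.04% | +1.9% / -2.0% |
| 4 h | +0.6% / -0.6% | -0.6% / +0.6% | +3.9% / -4.0% |
| 8 h | +3.3% / -3.1% | -3.2% / +3.2% | +8.1% / -7.7% |
| 12 h | +7.1% / -6.2% | -6.7% / +6.6% | +12.7% / -11.1% |

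As a cross-check, a profile whose late phase carries 30-80% of AUC, with the slope on three or five points and a 20% rise at 25:00, gives AUC0-inf +0.4 to 1% (4 h), +2 to 5.5% (8 h) and +7 to 21% (16 h). No half-life and no perturbation size is in the documents; all of these are assumptions.

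**Extrapolated share of iv AUC0-inf by choice of last sample** (mono-exponential):

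| Assumed t1/2 | Last sample 25:00 | Last sample 23:55 | 25:00 omitted (last is 13:00) |
|---|---|---|---|
| 8 h | 12.6% | 13.9% | 36% |
| 12 h | 25.2% | 26.8% | 50% |

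**The case against.** The strongest reply is that no mechanism is documented. Section 2.1 describes a change between Day 1 and Day 28, not within an hour of a second tablet. Slower elimination or displacement of bound tracer would be a hypothesis. This stands: the effect may be nil and its sign is unknown, so a reader should not infer that Day 1 F is understated. Nor does the 200-fold mass ratio (10 mg against 50 µg) help, since the same ratio applies to the first tablet by design.

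Second, the design seems to expect a short Day 1 half-life. Day 1 oral sampling stops at 8:00. With mono-exponential decline from a 1 h peak, the post-peak AUC beyond 8:00 is 2^(-7/t1/2): 9% at 2 h and 20% at 3 h, but 55% at 8 h and 67% at 12 h. If the half-life is 4 h or less, the effect on F is trivial; if it is 8 h or more, oral extrapolation is the larger problem for Day 1 F. This is inference, but it rightly limits the weight of the point.

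Third, slope points are chosen under a sponsor SOP that is not in the documents, and SAP Section 7.4 has a flag that removes a value from the half-life calculation. This stands in part: the flag is generic, is not pre-specified for 25:00, and leaves the value in all other analyses.

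Two stronger readings are tempting but unsupported. One is that any bias is shared by all subjects and hence hidden from the confidence interval. Footnote 10 makes analysis of this sample subject-specific, and its value must also be quantifiable. The other is that Day 1 and Day 28 are made unlike, because no tablet precedes 673:00. The two days are analysed separately, and 25:00 and 673:00 are both exactly 24 h after infusion start.

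**Conclusion.** The timing is established: as scheduled, the last Day 1 tracer sample follows the second 10 mg tablet by 1 h, and neither document keeps it out of the iv slope or AUC0-inf. A bias is possible but not shown. It requires an effect of the tablet on tracer disposition within 1 h, a 6:15 level above LOQ, a quantifiable 25:00 value, and use of that value in the slope. On those terms, a 10% change at 25:00 is negligible for F at an assumed half-life of 2-4 h (0.04-0.6%). It is about 3% at 8 h and 6-7% at 12 h, in either direction, with t1/2 moving by about 2-13%. In an exploratory estimation trial this is a cheap improvement to the denominator of a primary estimate, not a flaw that invalidates it.

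**What to change.** In the Day 2 Flow Chart, schedule the last Day 1 [C-14] sample immediately before the Day 2 tablet, for example at 23:55, instead of at 25:00. Leave the tablet time unchanged. State the order of sample and tablet in the 24:00 row, and say whether the sample enters the Day 1 terminal slope and AUC0-inf.

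Cost: one tube moves about 1 h earlier while the subject is still in-house, with no extra blood, visit or assay. Tracer follow-up is about 1 h shorter, which raises the extrapolated share only slightly (12.6% to 13.9% at an assumed 8 h half-life). The exact nominal match to 673:00 on Day 28 is lost.

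For samples already taken, record for each subject whether 25:00 preceded or followed the tablet. Any Day 1 iv analysis without 25:00 should be labelled supportive and shown with the extrapolated AUC fraction. Omitting the point makes 13:00 the last sample and raises extrapolation to about 36% at 8 h, so a difference between the two results could reflect the lost terminal phase rather than the second tablet.
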